7.1.6. Summaries of Adverse Events and Deaths

Treatment-emergent AEs will be summarized based on the Safety Analysis Set.

7.1.6.1. Summaries of AE Incidence by Severity

The number and percentage of subjects who experienced at least 1 TEAE will be provided and summarized by SOC, HLT, and PT. For other AEs described below, summaries will be provided by SOC, PT, and maximum severity:

- TEAEs
- Grade 3 or higher TEAE
- TEAEs related to ENTO
- TE SAEs

- TE SAEs related to ENTO
- TEAEs leading to ENTO discontinuation
- TEAEs leading to ENTO dose reduction or interruption

For AEs described below, summaries will be provided by SOC and PT:

- TEAEs
- TEAEs related to ENTO
- TE SAEs
- TE SAES related to ENTO
- TEAEs leading to ENTO discontinuation
- TEAEs leading to death

A brief, high-level summary of TEAEs described above will be provided by the number and percentage of subjects who experienced the above TEAEs. This summary table will also include TEAE related to chemotherapy (Groups A and B), Grade 3 or higher TEAE related to ENTO, Grade 3 or higher TEAE related to chemotherapy (Groups A and B), TE SAEs related to chemotherapy (Groups A and B), TEAEs leading to chemotherapy discontinuation (Groups A and B), TEAE leading to chemotherapy dose reduction or interruption (Groups A and B), and death.

Multiple events will be counted only once per subject in each summary. Adverse events will be summarized and listed first in alphabetic order of SOC and HLT within each SOC (if applicable) and then by PT in descending order of total frequency within each SOC. For summaries by severity, the most severe severity will be used for those AEs that occurred more than once in a given subject during the study.

In addition to the above summary tables, TEAEs and TE SAEs will be summarized by PT only in descending order of total frequency.

In addition, data listings will be provided for the following:

- All AEs, indicating whether the event is treatment emergent
- SAEs
- Deaths
- TEAEs leading to ENTO discontinuation

7.1.6.2. Summary of Deaths

A summary (number and percentage of subjects) of deaths will be provided. The summary will include the following categories:

- All deaths
- Deaths within 30 days of the last dosing of study drug
- Deaths beyond 30 days of the last dosing of study drug

The attribution of death will also be summarized.

7.1.7. Dose Limiting Toxicity

DLT will be analyzed with the DLT Analysis Set.

A listing of the DLT AEs will be provided by treatment group, dose level, subject ID, DLT category, preferred term, associated severity grade, and date of onset/resolution, if available.

A summary of DLT will be presented by SOC and PT.

7.2. Laboratory Evaluations

Local laboratory data collected during the study will be analyzed and summarized using both quantitative and qualitative methods. Summaries of laboratory data will be provided for the Safety Analysis Set. The analysis will be based on values reported in conventional units. When values are below the LOQ, they will be listed as such, and the closest imputed value will be used for the purpose of calculating summary statistics as specified in Section 3.7. Hemolyzed test results will not be included in the analysis, but they will be listed in by-subject laboratory listings.

A by-subject listing for laboratory test results will be provided by subject ID number and time point in chronological order for hematology, serum chemistry, coagulation, urinalysis, and serology separately. Values falling outside of the relevant reference range and/or having a severity grade of 1 or higher on the CTCAE severity grade will be flagged in the data listings, as appropriate.

7.2.1. Summaries of Numeric Laboratory Results

Descriptive statistics will be provided for each laboratory test specified in the study protocol as follows:

- Baseline values
- Values at each postbaseline visit
- Postbaseline maximum value
- Postbaseline minimum value
- Change from baseline to postbaseline maximum value
- Change from baseline to postbaseline minimum value

A baseline laboratory value will be defined as the last measurement obtained on or prior to the date/time of first dose of study drug. Change from baseline to a postbaseline visit will be defined as the visit value minus the baseline value. The mean, median, Q1, Q3, minimum, and maximum values will be displayed to the reported number of digits; StD values will be displayed to the reported number of digits plus 1.

In the case of multiple values in an analysis window, data will be selected for analysis as described in Section 3.8.3.

7.2.2. Graded Laboratory Values

CTCAE Version 4.03 will be used for assigning toxicity grades (0 to 4) to laboratory results for analysis. Grade 0 includes all values that do not meet the criteria for an abnormality of at least Grade 1. For laboratory tests with criteria for both increased and decreased levels; analyses for each direction (ie, increased, decreased) will be presented separately.

7.2.2.1. Treatment-Emergent Laboratory Abnormalities

Treatment-emergent laboratory abnormalities are defined as values that increase at least 1 toxicity grade from baseline at any postbaseline time point, up to and including the date of last dose of study drug plus 30 days. If the relevant baseline laboratory value is missing, any abnormality of at least Grade 1 observed within the time frame specified above will be considered treatment emergent.

7.2.2.2. Summaries of Laboratory Abnormalities

The summary (number and percentage of subjects) for treatment-emergent laboratory abnormalities will be provided by lab test; subjects will be categorized according to the most severe postbaseline abnormality grade for a given lab test.

For all summaries of laboratory abnormalities, the denominator is the number of subjects with nonmissing postbaseline values up to 30 days after last dosing date.

A by-subject listing of treatment-emergent laboratory abnormalities will be provided by subject ID number and time point in chronological order. This listing will include all test results that were collected throughout the study for the lab test of interest, with all applicable severity grades displayed.

7.2.3. Shift in CTCAE Grade Relative to Baseline

Shift tables will be presented by showing change in CTCAE grade from baseline to the worst postbaseline grade up to 30 days after last dosing date. The percentage will be based on subjects with values available at both baseline and postbaseline.

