Toxicities that require temporary interruption of treatment with ENTO (but not permanent discontinuation) will not be considered DLT unless the toxicity does not resolve to \leq Grade 2 in 10 days.

In subjects with < 5% blasts in the bone marrow, absence of myelodysplastic changes, and/or absence of AML by flow cytometry in the bone marrow, hematologic toxicity will be defined as: failure to recover neutrophil count ($ANC > 500/\mu L$) or platelet count ($> 25000/\mu L$) within 4 weeks after achieving < 5% blasts in Group A and Group C. Hematologic toxicities will not be used to assess DLTs in Group B.

3.2.1. Guidelines for Phase 1b Dose Escalation and Phase 2 Group B Dose Expansion

In Phase 1b, the trial employs the standard NCI definition of MTD (starting dose associated with DLT in <33.3% of subjects during the DLT assessment window). After considering the available safety and efficacy data and in consultation with the study PI, a dose at or below MTD will be chosen by the sponsor for further evaluation.

Dose escalation for Groups A, B, and C will proceed independently and in parallel per [Table 3-6](#).

Table 3-6. Dose Escalation/ DLT Guidelines

Number of Subjects with DLT at a given level	Escalation Decision Rule
0 out of 3	Enroll 3 subjects at the next dose level. An additional 3 subjects can be enrolled at the current dose level without a DLT if additional evaluation is warranted after discussion with the study PI and medical monitor.
≥ 2	Dose escalation will be stopped. This dose level will be declared maximally administered dose (highest dose administered). Three (3) additional Pts. will be entered at next lower dose level if only 3 subjects were treated previously at that dose.
1 out of 3	Enroll at least 3 more subjects at this dose level. If 0 of these 3 subjects experience DLT, proceed to the next dose level. If 1 or more of this group suffer DLT, then dose escalation is stopped, and this dose is declared the maximally administered dose. Three (3) additional subjects will be entered at the next lower dose level if only 3 subjects were treated previously at that dose.
≤ 1 out of 6 at highest dose level below the maximally administered dose	This is the maximum tolerated dose (MTD) and generally the effective dose. At least 6 subjects must be entered at the effective dose. The recommended expansion dose may be a dose lower than the MTD.

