8.6.3. Laboratory Evaluations

All laboratory data will be listed. Summaries of laboratory data will be based on observed data and will be reported using conventional units. The focus of laboratory data summarization will be on treatment-emergent laboratory abnormalities. A treatment emergent laboratory abnormality is defined as an abnormality that, compared to baseline, worsens by ≥ 1 grade in the period from the first dose of study treatment to 30 days after the last dose of study treatment. If baseline data are missing, then any graded abnormality (ie, an abnormality that is Grade ≥ 1 in severity) will be considered treatment emergent. Laboratory abnormalities that occur before the first dose of study treatment or > 30 days after the subject has been discontinued from study treatment will be included in data listings.

Hematological, serum biochemistry, and urine data will be programmatically graded according to CTCAE severity grade, when applicable. For parameters for which a CTCAE scale does not exist, reference ranges from the central laboratory will be used to determine programmatically if a laboratory parameter is below, within, or above the normal range for the subject's age, sex, etc.

Hematological and serum biochemistry and their changes from baseline will be summarized. Summary tables will be presented for each relevant assay to show the number of subjects by CTCAE severity grade with corresponding percentages. For parameters for which a CTCAE scale does not exist, the frequency of subjects with values below, within, and above the normal ranges will be summarized. Subjects will be characterized only once for a given assay, based on their worst severity grade observed during a period of interest (eg, during the study or from baseline to a particular visit).

Shift tables for hematology and serum biochemistry will also be presented by showing change in CTCAE severity grade from baseline to each visit. For parameters for which a CTCAE scale does not exist, shift tables will be presented showing change in results from baseline (normal, low and high [or abnormal]) to each visit (normal, low and high [or abnormal]). Tables will be prepared to show frequencies adjusted for baseline values; for this frequency, subjects with the same or worse toxicity grade at baseline are not considered.

Separate listings and summaries will be prepared for laboratory abnormalities that are Grade ≥ 3 in severity.

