In the Group B Phase 2, approximately 40 additional subjects will be randomized in a 1:1 manner to either treatment arm ENTO + decitabine or ENTO + azacitidine. Randomization will be stratified by age (≤ 75 years or > 75 years) and WBC ($\leq 5,000/uL$ or $> 5,000/uL$). Assuming a composite complete remission rate of 50% for both treatment arms, the 90% CI would be 30% to 70% with a sample size of 20. The composite complete remission rate of standard chemotherapy is reported as 20% to 30%. Evaluation between the treatment arms will be based on the totality of clinical data.

Approximately 63 additional subjects will be enrolled in Group C dose expansion.

A total of 15 initial subjects, including 9 subjects in Group C Phase 1b who were R/R AML and received at least 21 days of ENTO (400 mg or 800 mg) and 6 subjects in Cohort C1A, will be pooled for evaluation of futility in subjects with R/R AML. An additional 15 subjects will be enrolled if greater or equal to 5 (out of 15) CR/CRi are observed. This futility boundary will provide a high chance (84%) of early stopping of the trial if the composite complete remission rate is undesirable (20%) and a low chance (22%) of early stopping if the composite complete remission rate is clinically meaningful (40%).

The sample size is 15 for Cohort C2. This sample size is based on practical considerations. The sample size is 30 for previously untreated AML (unfit for Group A or B), including 3 subjects in Group C Phase 1b who were previously untreated AML, unfit for Group A or B, and received at least 21 days of ENTO (400 mg or 800 mg), and 27 subjects in Cohort C3, which will provide adequate precision of efficacy estimates. [Table 1-3](#) provides the 90% CI of 30 subjects for the assumed composite complete remission rate.

Table 1-3. Exact 90% CIs of Composite Complete Remission Rate for a Cohort Size of 30 in Subjects with Previously Untreated AML (Unfit for Group A or B)

Assumed Composite Complete Remission Rate of ENTO Monotherapy in Subjects with Previously Untreated AML (Unfit for Group A or B)	Exact 90% CI
30%	(17% – 47%)
50%	(34% – 66%)
70%	(53% – 83%)

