7.7. Changes From Protocol-Specified Safety Analyses

For Groups A and B, safety data will not be presented by the lead-in ENTO therapy phase and the induction chemotherapy phase separately due to no washout period.

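### SAP 7.2.3 replaces the protocol's baseline-to-each-visit laboratory shift tables with one shift to worst grade, and SAP 7.7 does not declare it; no graded laboratory summary then shows persistence or recovery

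*SAP*

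**What the plan says.** Protocol 8.6.3 plans three kinds of categorical laboratory table:

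- A summary that counts each subject once per assay, "based on their worst severity grade observed during a period of interest".
- Grade shifts: "Shift tables for hematology and serum biochemistry will also be presented by showing change in CTCAE severity grade from baseline to each visit".
- For tests without a CTCAE scale, "shift tables will be presented showing change in results from baseline (normal, low and high [or abnormal]) to each visit".

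SAP 7.2.3 has a single shift table: "change in CTCAE grade from baseline to the worst postbaseline grade up to 30 days after last dosing date". It has no by-visit version and no shift table for tests without a CTCAE scale. SAP 7.2.2.2 separately summarises each subject's most severe postbaseline grade for each test.

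SAP 7.7 records a single departure from the protocol, which concerns only the two combination-therapy groups: "safety data will not be presented by the lead-in ENTO therapy phase and the induction chemotherapy phase separately due to no washout period". The shift tables are not mentioned.

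On how blood counts are used, Protocol 3.2 says for Group B that "Hematologic toxicities will not be used to assess DLTs in Group B". SAP 1.3 says of the randomised Group B arms that "Evaluation between the treatment arms will be based on the totality of clinical data".

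**The concern.** A protocol-specified safety table has been cut without a record, and its replacement adds little beyond SAP 7.2.2.2. What is lost is grade over time.

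The protocol itself treats time as the relevant dimension. In Groups A and C the hematologic DLT is failure of counts to recover within 4 weeks of reaching under 5% blasts, not depth of nadir. Group B has no hematologic DLT, so no DLT summary covers marrow recovery there. Whether a liver-test abnormality counts as a DLT depends on whether it resolves (Protocol 3.2), and indirect bilirubin rises on ENTO are described as mostly self-limiting (Protocol 1.10.2). A worst-grade table records none of this. Protocol 4.1 also admits subjects with any degree of cytopenia caused by the malignancy. A subject at Grade 4 at baseline cannot shift upward, and a worst-grade table cannot show improvement in that subject.

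SAP 7.7 drops the split between lead-in and induction as well. With by-visit shifts also gone, no graded laboratory summary shows what happened before chemotherapy began.

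**Working it through.** **1. Set the texts side by side.**

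| Table | Protocol 8.6.3 | SAP 7.2 | Declared in SAP 7.7? |
|---|---|---|---|
| Worst grade per subject and test | yes | yes (7.2.2.2) | no change |
| Grade shift, baseline to each visit | yes | no | no |
| Low/normal/high shift to each visit, tests without a CTCAE scale | yes | no | no |
| Grade shift, baseline to worst | not specified | yes (7.2.3) | no |

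**2. How much is collapsed.** Protocol 6.3.2 schedules Group B hematology on Days 8 and 28 of each induction cycle, for 2 to 4 cycles. That is 2 × 2 = 4 to 2 × 4 = 8 graded values per subject, reduced to one.

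**3. What the other outputs give.** SAP 7.2.1 gives numeric values at each visit, but change from baseline only to the maximum and minimum. SAP 7.2.4 plots individual blasts, neutrophils, platelets and WBC, and only through induction in Groups A and B. The SAP 7.2.2.2 listing shows grades in date order but is not a summary. SAP 7.6 counts platelet transfusions by cycle. None gives the number at Grade 3-4 at a visit by baseline grade.

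**4. Does a worst-grade table hide a difference between the Group B arms?** The documents do not say how often the worst blood-count grade is 4. The nearest figure is Protocol 1.3.1: Grade 3 or higher febrile neutropenia in 41/53 = 77.4% of Group A subjects (exact 95% CI 63.8% to 87.7%). That is neither a worst neutrophil or platelet grade nor Group B.

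As an illustration only, let q be the assumed chance of Grade 4 at one visit and k the number of visits, treated as independent. Then P(worst grade 4) = 1 − (1 − q)^k. For q = 30% and k = 8, this is 1 − 0.7^8 = 94.2%. Power is for 20 per arm, two-sided 0.05, by a normal approximation that is rough near 100%.

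| q in the two arms | One visit: difference, power | Worst of 4 visits | Worst of 8 visits |
|---|---|---|---|
| 20% v 40% | 20 points, 0.28 | 59% v 87%, 28 points, 0.51 | 83% v 98%, 15 points, 0.37 |
| 30% v 50% | 20 points, 0.25 | 76% v 94%, 18 points, 0.34 | 94% v 99.6%, 5 points, 0.16 |
| 30% v 60% | 30 points, 0.48 | 76% v 97%, 21 points, 0.52 | 94% v 99.9%, 6 points, 0.18 |

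The worst-grade table does worse than a single visit in two of six cases, both with Grade 4 near-universal. In the other four it does as well or better. Positive correlation between visits would lower the worst-grade percentages, so these figures lean towards saturation.

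**5. Precision in Group B.** SAP 1.3 gives a 90% CI of 30% to 70% for a 50% rate with 20 subjects. The exact interval for 10/20 is 30.2% to 69.8%, which agrees. A by-visit proportion near 50% would be as imprecise, and more so in practice because SAP 1 says Group B Phase 2 closed before its planned size.

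**The case against.** The strongest reply is that this is a documentation gap in one descriptive table and that much of the time course survives.

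- By-visit quartiles can be read against the Grade 4 limits in Protocol 3.3 (neutrophils below 500/µL, platelets below 25,000/µL). A median below the limit shows that at least half the subjects are at Grade 4.
- CR and CRi rates show incomplete count recovery among remitters.
- AE tables report severity.
- Both Group B arms receive ENTO, so no shift table isolates its effect. Low counts may reflect active leukemia, and one Day 28 value is not a duration.

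Most of this stands and limits the weight of the point. It does not remove it. Quartiles bound the proportion only at 25%, 50% and 75%, and not by baseline grade. CRi covers remitters only. The AE tables use maximum severity, and Protocol 7.1.3 keeps laboratory abnormalities without clinical significance out of the AE record.

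A reader might infer that the worst blood-count grade is nearly always 4, or that the SAP table cannot separate the Group B arms. The documents support neither. No figure for worst grade is given, and the working shows that a worst-grade table may fail to distinguish the arms if Grade 4 is near-universal but can otherwise do as well as a single visit. Nor is the time course lost altogether; what is lost is its tabulation by grade.

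**Conclusion.** The point holds as an undeclared reduction of a protocol-specified safety analysis. That conclusion rests on the text alone and needs no assumption about how often Grade 4 occurs. Two protocol tables are absent from the SAP: the by-visit grade shift and the by-visit shift for tests without a CTCAE scale. The substitute cannot show whether graded cytopenia or liver-test abnormalities persist or resolve, and no other planned output tabulates this by baseline grade.

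The weight is modest. Safety is a primary objective, but these tables are descriptive, and no efficacy endpoint, sample size, error rate or decision rule depends on them. Any gain in comparing the Group B arms is conditional and would be imprecise at 20 or fewer per arm.

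**What to change.** In SAP 7.2.3, keep the worst-grade shift and restore the by-visit grade shift, at least for neutrophils, platelets, ALT, AST and bilirubin, at these nominal visits:

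- **Group B:** Day 28 of each induction cycle, by arm for the randomised part.
- **Group C:** Cycle 1 Days 8, 14 and 28.
- **Group A:** Day 14 of Cycle 1 and, if given, of Cycle 2. Protocol 3.1.1 and 3.1.2 place the count nadir at Cycle 1 Day 14, so for blood counts this visit says little about recovery.

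List in SAP 7.7, with a reason, every visit or test still left out, including the shift tables for tests without a CTCAE scale.

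All these visits are scheduled, so the nominal-visit rule in SAP 3.8.2 applies and no new window is needed. The grades are already assigned under SAP 7.2.2. The cost is SAP wording and longer output: for five tests, 4 × 5 = 20 panels in Group B, 3 × 5 = 15 in Group C and 2 × 5 = 10 in Group A, or 45 before splitting by table column. SAP 1 says the plan is finalised before the database is, so the change belongs before that point.

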7.2.4. Graphics of Numeric Laboratory Results

Spaghetti plots of circulating blasts (%), neutrophils, platelets, and WBC through the induction treatment for Group A and Group B and all cycles for Group C will be provided. Since different subjects will be treated for different time periods per cycle and different number of cycles, the x-axis of the spaghetti plot, which is the study day, will be adjusted following the algorithms in Section 6.4 to distinguish laboratory results among the cycles.

7.3. Body Weight and Vital Signs

Descriptive statistics will be provided for body weight and vital signs as follows:

- Baseline value
- Values at each postbaseline visit
- Postbaseline maximum value
- Postbaseline minimum value
- Change from baseline to postbaseline maximum value
- Change from baseline to postbaseline minimum value

A baseline value will be defined as the last available value collected on or prior to the date/time of first dose of study drug. Change from baseline to a postbaseline visit will be defined as the postbaseline value minus the baseline value. Body weight and vital signs measured at unscheduled visits will be included for the baseline value selection.

In the case of multiple values in an analysis window, data will be selected for analysis as described in Section 3.8.3. No formal statistical testing is planned.

A by-subject listing of vital signs will be provided by subject ID number and time point in chronological order. Body weight will be included in the vital signs listing.

